3.1 Cut-off date used for the analysis

The data base lock date will be the cut-off date used for the final clinical study report (CSR).

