This statistical analysis plan (SAP) describes all planned analyses for the clinical study report (CSR) of study CPKC412E2301: a phase III, randomized, double-blind clinical trial of chemotherapy with daunorubicin or idarubicin and cytarabine for induction and intermediate dose cytarabine for consolidation plus midostaurin (PKC412) or placebo in newly diagnosed patients with FLT3-MN (SR<0.05) AML (FLT3 mutant to wild type signal ratio below the 0.05 clinical cut-off).

The content of this SAP is based on protocol CPKC412E2301 amendment 1. All decisions regarding final analysis, have been made prior to final database lock but after unblinding of the study data.

The first interim analysis of the primary endpoint (Event Free Survival (EFS)) for futility has been performed and the study was stopped due to lack of efficacy on 23-Sep-2019 based on DMC recommendation. Subsequently, investigators were notified on the futility outcome and study was unblinded not only for Novartis but also the investigators. While majority of patients discontinued from the study within subsequent weeks, some patients decided to continue protocol planned study treatment. This SAP now describes the analyses for the final CSR which will be generated when all patients discontinued study treatment.

The originally planned efficacy and safety analyses are reduced based on the futility outcome. However, some subgroup analyses have been added (e.g. safety and efficacy by anthracyclin for AML induction therapy (Daunorubicin vs Idarubicin)) and some analyses are only performed now for the final CSR (e.g. QoL, PK, [REDACTED]).

2 Study design, objectives and endpoints

[figure not shown]
This is a randomized, double-blind, multi-center, placebo-controlled phase III study using a group sequential design with two interim analyses for the primary endpoint event-free survival (EFS) and regular safety looks. The study population comprises 502 adult patients with newly diagnosed FLT3-MN (SR<0.05) AML. Patients will be stratified according to age (<60 vs. ≥ 60 years) and will be randomized in a 1:1 ratio into one of two treatment arms:

- Midostaurin + chemotherapy

Or

- Placebo + chemotherapy

Figure 2-1 Study design

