To compare the time to platelet recovery in the two treatment groups.	Number of days from the first day of a chemotherapy cycle to first day platelets $\geq 50 \times 10^9/L$. Number of days from day 1 of commencing induction therapy to first day platelets $\geq 100 \times 10^9/L$.
To assess the safety and tolerability of midostaurin in combination with chemotherapy and as monotherapy during post-consolidation.	Frequency/severity of AEs, and laboratory abnormalities.
To further characterize the pharmacokinetics of midostaurin, CGP52421 and CGP62221.	Plasma concentrations and pharmacokinetic parameters for midostaurin, CGP52421 and CGP62221.
To assess the impact of midostaurin on health related quality of life and AML symptom reduction.	Change from baseline score for each time point for the FACT-Leu and the EQ5D-5L (visual analogue scale (VAS)) by treatment arm.

[REDACTED]

[REDACTED]

[REDACTED]

[REDACTED]

[REDACTED]

[REDACTED]

[REDACTED]

[REDACTED]

[REDACTED]

[REDACTED]

[REDACTED]

[REDACTED]

[REDACTED]

Data analysis general information

The statistical analysis of this study will be performed by Novartis. SAS® version 9.4 or later (SAS Institute Inc., Cary, NC, USA) will be used for all analyses. All data are part of the Clinical Database and will be exported to SAS® files for analysis. EAST version 6.4 or later (Cytel Inc.®) will be used to determine stopping boundaries in the group sequential plan.

The final EFS analysis was supposed to be performed by Novartis. However, since the study was stopped at first interim analysis only an updated EFS analysis will be provided in the final CSR. The first interim analysis of EFS was performed by an independent external statistician and an independent external programmer (CRO not involved with the conduct of the study). The study was stopped at this first interim and no further analyses are to be performed (i.e. study stopped).

The study will end when the last ongoing patient will have completed or discontinued treatment.

All events with start date before or on the cut-off date and end date after the cut-off date will be reported as 'ongoing'. The same rule will be applied to events starting before or on the cut-off date and not having documented end date. This approach applies, in particular, to adverse event and concomitant medication reports. For these events, the end date will not be imputed and therefore will not appear in the listings.

General analysis conventions

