6.8 Dose reductions, interruptions or permanent discontinuations

‘Dose changed’, ‘Dose interrupted’, and ‘Dose permanently discontinued’ fields from the exposure eCRF pages will be used to determine the dose reductions, dose interruptions, and permanent discontinuations, respectively.

The corresponding fields ‘Reason for dose change/dose interrupted’ and ‘Reason for permanent discontinuation’ will be used to summarize the reasons.

A dose change is either ‘change in prescribed dose level’ or ‘dosing error’ where actual dose administered is different from the prescribed dose.

For the purpose of summarizing interruptions and reasons, in case multiple entries for interruption that are entered on consecutive days with different reasons will be counted as separate interruptions. However, if the reason is the same in this block of entries, then it will be counted as one interruption.

Reduction: A dose reduction is, where the prescribed dose level is lower than the previous prescribed dose level or where the actual dose administered is lower than the calculated dose amount based on the prescribed dose. Therefore any dose change to correct a dosing error will not be considered a dose reduction. Only dose change is collected in the CRF, number of reductions will be derived programmatically based on the change and the direction of the change. In addition, if a patient moves to a less frequent regimen, such changes will then be counted as dose reductions.

7 Analysis of the primary objective

The primary objective of this study was to determine if the addition of midostaurin to standard induction and consolidation therapy, followed by single agent post-consolidation therapy improves event-free survival (EFS) in patients with newly diagnosed FLT3-WT AML.

As the study concluded at the first efficacy interim analysis due to futility, the endpoints will be derived and summarized based on the final data, but no testing (p-values) will be provided in the final CSR.

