8.3 Analysis of secondary endpoints

The secondary efficacy variables include CR or CRi with adequate blood count recovery rate, MRD, DFS, CIR and CID. The assessment of these endpoints, except MRD, will be based on the IWG criteria for AML [[Cheson et al 2003](#), [ELN 2017 / Döhner et al 2017](#)] as per investigator assessment. All these endpoints will only be descriptively summarized with 95% CIs but without any p-values.

The rate of CR/CRi with adequate blood count recovery will be analyzed based on the FAS. However, DFS, Cumulative Incidence of Relapse (CIR) and Cumulative Incidence of Death (CID) will be analyzed based on data from responders (CR or CRi with adequate blood count recovery within 93 days after start of treatment) in the FAS. Assessment of relapse from CR or CRi with adequate blood count recovery, DFS, CIR and CID will not consider whether a patient received HSCT. All secondary analyses will include all data observed up-to the cut-off date, unless otherwise specified.

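### Database lock is the only cut-off, so overall survival (OS) in the final report is exposed to informative censoring after the futility stop, with no stop-date analysis planned

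*SAP*

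**What the plan says.** SAP section 1 records that "the study was stopped due to lack of efficacy on 23-Sep-2019 based on DMC recommendation" and continues: "Subsequently, investigators were notified on the futility outcome and study was unblinded not only for Novartis but also the investigators". On who remained it says: "While majority of patients discontinued from the study within subsequent weeks, some patients decided to continue protocol planned study treatment". SAP section 2 (data analysis general information) sets the end of the study by treatment: "The study will end when the last ongoing patient will have completed or discontinued treatment".

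SAP 3.1 then gives the single cut-off: "The data base lock date will be the cut-off date used for the final clinical study report (CSR". Section 7 says of the primary analysis that "the endpoints will be derived and summarized based on the final data", and 8.3 says: "All secondary analyses will include all data observed up-to the cut-off date, unless otherwise specified". For OS, sections 3.7 and 8.1 censor a patient not known to have died at the last contact on or before that cut-off. Adverse events are summarised from first dose to 30 days after last dose (3.6.2, 9.2), with no division at unblinding.

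The readable SAP text contains no analysis cut at the stop or unblinding date and no display by period. Sections 7, 8.2 and 8.3 make the efficacy results descriptive, without p-values, but hazard ratios, 95% intervals, medians and Kaplan-Meier estimates are still reported.

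**The concern.** Protocol 4.4 assumed that every patient would stay in treatment or follow-up until the data cut-off. Under that premise a late cut-off censors administratively: follow-up ends at a date unrelated to the patient's condition. The premise failed when most patients left after the stop, yet the cut-off stayed late.

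Who could continue treatment is not random. Protocol 4.5 offers completion after a futility stop to patients still on treatment whom the investigator judges to benefit. Protocol 7.1.4 requires treatment to end on induction failure or relapse. Continuers are therefore patients who have neither failed nor relapsed. Failed and relapsed patients were in survival follow-up only, and if they left they are censored for OS just when their risk of death is highest. Kaplan-Meier and Cox estimates assume that those censored have the same later risk as those still observed.

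At stake are the OS curves, medians and hazard ratio, including the subgroup forest plots. A separate and smaller point is that relapse is investigator-assessed, so relapse calls and adverse-event causality are open-label after unblinding.

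**Working it through.** **1. What the stop rested on.** The plan gives no figure for the cut-off question itself. Its nearest figure is the updated futility boundary, HR 0.91 at 145 events (SAP 9.13.1). With t = 145/285 = 0.509, beta spent is 0.1 × (1 − e^(1.2t)) / (1 − e^1.2) = 0.0363, whose normal quantile is −1.796. The drift is √(145/4) × −ln(0.675) = 2.366. The boundary is z = 2.366 − 1.796 = 0.571, and HR = exp(−2 × 0.571/√145) = 0.91. The same formula at 114 events gives 0.97. Both agree with the SAP. The futility decision therefore rests on the interim data and does not depend on SAP 3.1.

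**2. Dates.** No patient was enrolled at protocol amendment 1 (08-Jun-2018). From then to 23-Sep-2019 is 472 days (15.5 months), the longest possible follow-up before the stop. From the stop to the SAP date, 11-Jan-2021, is 476 days; lock is no earlier, since the SAP states that its decisions precede lock. Every point on the OS curve beyond 472 days therefore comes entirely from follow-up after the stop. Protocol 10.9 expects a control median OS of 30 months, and 472 + 476 = 948 days is 31.1 months. If that expectation is right, the lock-date median is read from post-stop data alone.

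**3. Illustrative model for OS.** All inputs are assumptions: uniform entry over 15 months, stop at 15.5, lock at 31.2; 35% induction failure; exponential times with median 20 months to relapse and 9 months from failure or relapse to death; no treatment effect. A stated share of patients in remission at the stop stay, and everyone else leaves within a month.

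True 16-month OS, with a = ln2/20 = 0.0347 and b = ln2/9 = 0.0770:

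- failures: 0.35 × e^(−16b) = 0.102
- responders: 0.65 × (b·e^(−16a) − a·e^(−16b)) / (b − a) = 0.524
- total: 0.626, or about 63%

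| Remission patients staying (midostaurin / placebo) | OS HR, lock cut-off | OS HR, stop cut-off |
|---|---|---|
| 30% / 30% | 1.00 | about 1 |
| 20/2, 30/5, 50/5, 50/20 | about 0.89 to 0.95 | about 1 |

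At 30%/30% the lock-date estimate of 16-month OS is about 67% in each arm, so the curve is too high even with equal staying. A stop-date cut brings the curve back to about the truth over the time it covers. Swapping the arms inverts the ratios: 1/0.95 = 1.05 and 1/0.89 = 1.12.

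**4. Other endpoints.** In the same model the DFS hazard ratio is 0.99 to 1.01 throughout. Failure and relapse are already events for EFS (SAP Table 7-1), and relapse is for DFS and CIR, so everyone still at risk is in remission. CID is less protected: SAP Table 8-5 counts a death after relapse as the event and a relapse without recorded death as competing, so classification depends on later follow-up.

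**5. A different assumed model.** Take 375 patients, a 30-month OS scale, gamma frailty with variance 1, about 9 to 20% of survivors staying, and a true HR of 1.0. The stop-date cut gives 0.99 to 1.02 in every scenario. The lock-date cut gives 1.00 when staying is unrelated to prognosis, or related equally in both arms. It gives 0.97, 0.89 and 0.77 as selection on prognosis differs increasingly by arm. Selection on prognosis of this kind, acting within remission, is what EFS or DFS bias would need.

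**The case against.** The strongest reply is that this matters little. The decision to stop came from the interim at 145 events, analysed by an independent external statistician. The SAP calls the final EFS result an update, and no efficacy hypothesis is tested. That stands: no trial decision turns on the cut-off. It does not make the reported OS curves, medians and intervals correct.

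A reader might infer more than the documents support:

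- **That EFS, DFS and adverse-event rates are distorted in the same way.** The mechanism does not reach EFS, DFS or CIR unless staying depends on prognosis within remission, which nothing documents. For adverse events, observing patients only to 30 days after last dose is the design in both periods.
- **That the hazard ratio is biased towards midostaurin.** This needs unequal staying by arm, and no counts are given. Placebo patients are not shown to have had little reason to stay: study treatment in both arms includes chemotherapy (SAP 3.2), and Protocol 4.5 offers continuation without regard to arm.
- **That only volunteers were still observed.** The SAP says most left and some continued treatment. It does not say that all off-treatment patients were lost, and section 4.5 still tabulates survival follow-up.
- **That the unblinded period is the longer one.** On the known bounds this is 476 against 472 calendar days. In patient-time the later period is probably the smaller. The unblinding date itself is not given, only that it followed the stop.

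Moving the main cut-off for every endpoint would also remove observed deaths and long-exposure safety data from the main tables, which the evidence does not require.

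**Conclusion.** The concern holds for OS. With lock as the only cut-off, censoring after the stop is likely informative, because treatment continuers are by rule neither failed nor relapsed while failed and relapsed patients may have left. Kaplan-Meier OS and medians would then be too favourable in both arms, by about 4 percentage points at 16 months in the illustration. The hazard ratio is biased only if staying differs by arm: 1.00 if equal, about 0.89 to 0.95 in the assumed unequal cases, and above 1 if more placebo patients stayed.

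These sizes rest on invented staying rates and event times. The actual size and direction cannot be derived from the documents. The conclusion also assumes that a material share of failed or relapsed patients left survival follow-up; if nearly all were followed to lock, the bias would be small. For EFS, DFS and CIR the supported point is narrower: assessment after unblinding is open-label, and no sensitivity analysis separates it, although Protocol 10.4.3 announced EFS analyses under alternative censoring.

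**What to change.** In SAP 3.1 and 8.2, add an OS analysis (hazard ratio, Kaplan-Meier, median) administratively censored at 23-Sep-2019 or at the date investigators were notified. Base the interpretation of OS on it and show the lock-date OS alongside. Give the same cut as a sensitivity analysis for EFS, DFS, CIR and CID. Report by arm how many patients continued after the stop. Flag adverse events with onset after unblinding as open-label.

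The cost is one date flag and a few extra tables, with no new data. Some late deaths fall outside the stop-date OS analysis. With at most 15.5 months of follow-up, its median may not be reached; if so, the report should say so and not take a median from the lock-date curve without comment.

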3.2 Study drug and study treatment

Study drug refers to Midostaurin (PKC412) or Placebo (PBO).

Study treatment refers to

- Midostaurin + Chemotherapy (idarubicin/daunorubicin, cytarabine) or
- Placebo + Chemotherapy (idarubicin/daunorubicin, cytarabine) (control group).

Study treatment components refer to

- Midostaurin/Placebo or
- Idarubicin/Daunorubicin or
- Cytarabine

Study drug combination partner refers to Idarubicin/Daunorubicin or Cytarabine

3.3 Date of first administration of study drug

The date of first administration of study drug is derived as the first date when a non-zero dose of study drug was administered and recorded on the exposure electronic case report form (eCRF). The date of first administration of study drug will also be referred as *start of study drug*.

3.4 Date of last administration of study drug

The date of last administration of study drug is defined as the last date when a non-zero dose of study drug was administered and recorded on the exposure electronic case report form (eCRF).

3.5 Date of first administration of study treatment

The date of first administration of study treatment is derived as the first date when a non-zero dose of any component of study treatment was administered and recorded on the exposure eCRF. For example, if the 1st dose of study drug A is administered on 04Jan2019, and the 1st dose of its combination partner, drug B, is administered on 03Jan2019, the date of the first administration of study treatment is on 03Jan2019). The date of the first administration of study treatment will also be referred as the *start of study treatment*.

3.6 Date of last administration of study treatment

The date of last administration of study treatment is derived as the last date when a non-zero dose of any component of study treatment was administered and recorded on exposure eCRF of any study treatment component. For example, if the last dose of Midostaurin is administered on 15Apr2019, and the last dose of a combination partner, e.g., Cytarabine, is administered on 17May2019, the date of last administration of study treatment is then on 17May2019.

3.6.1 Baseline

Baseline is the result of an investigation describing the “true” uninfluenced state of the subject.

For *efficacy evaluations*, the last assessment before or at the date of randomization is taken as the “baseline” value or assessment, if available.

In the context of a baseline definition, ECOG PS assessment as well as all PRO variables will follow the efficacy rule, irrespective of addressing quality of life or disease symptoms.

For PRO completion summary and PROs, baseline is defined by instrument and scale for QOL and by instrument for QUE. For QUE, the last “partially” completed (or better) answer will be used for baseline in case of more than 1 baseline assessment. In case of >1 non-completed answers (whatever reason), the last answer will be used. For QOL, the last assessment with non-missing score within eligible baseline visit per scale/category will be used as baseline for that

scale. For Global Severity questionnaire the baseline is defined by instrument; the last available assessment per baseline will be used.

For *safety evaluations* (e.g. laboratory and ECG), the last available assessment *before or at the date the study treatment* administration will be used as the “baseline” assessment.

If patients have no value as defined above, the baseline result will be considered to be missing.

3.6.2 On-treatment assessment/event

All on-treatment assessments/events are any assessments/events obtained in the time interval:

[Date of first administration of study treatment; date of last administration of study treatment +30 days], i.e., inclusive lower and upper limit.

The calculation of study treatment duration may use different rules as specified in [Section 6.1](#).

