4.2.2 Consolidation phase

Patients achieving CR or CRi with adequate blood count recovery after induction with one or two cycles of induction therapy will proceed to consolidation therapy with either 3 or 4 cycles of intermediate-dose cytarabine respectively, or to HSCT with or without preceding consolidation cycles. Patients may undergo transplantation at the discretion of the Investigator (refer to 2017 ELN and 2016 National Comprehensive Cancer Network (NCCN) recommendations). In patients who are treated with allogeneic HSCT instead of consolidation therapy or after start of consolidation therapy the conditioning regimen and management after transplantation will be according to local institutional standards. Study treatment will be interrupted at least 48 hours before the initiation of the transplant conditioning regimen. Patients with transplantation and recovery from the procedure will not receive further cycles of consolidation treatment but receive post-consolidation treatment with study drug. They can start the post-consolidation therapy not earlier than 30 days after transplant but not later than 100 days after transplant.

Patients will receive midostaurin (two 25 mg capsules) or placebo (2 capsules) twice daily orally from day 4 until 48 hours prior to the start of the next consolidation cycle.

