4.2.3 Post-consolidation phase

After adequate blood count recovery following the final cycle of consolidation therapy, patients will receive 12 cycles (28 days/cycle) of continuous therapy with midostaurin or placebo twice daily at 50 mg.

Patients who underwent HSCT after achieving CR or CRi with adequate blood count recovery will receive midostaurin or placebo 50 mg twice daily as post-consolidation therapy, continuously, for up to 12 cycles (28 days/cycle). Post HSCT post-consolidation therapy will begin >30 days but not later than 100 days following HSCT.

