6.3 Dose modifications

6.3.1 Dose modification and dose delay

For patients who do not tolerate the protocol-specified dosing schedule, dose interruptions and/or reductions are either recommended or mandated in order to allow patients to continue the study treatment.

These dose modifications are summarized in [Table 6-2](#). Deviations to mandatory dose interruptions and/or reductions are not allowed. Permanent treatment discontinuation is mandatory for specific events indicated as such in [Table 6-2](#).

These dose changes must be recorded on the appropriate CRF.

Study drug (midostaurin/placebo)

[Table 6-2](#) describes toxicities (i.e., adverse drug reactions), laboratory values, or other assessments that require interruption or dose modification of study drug. Whether an AE that is not considered to be caused by the study treatment requires modifications needs to be assessed by the investigator. The need for modification in case of non-drug related AEs depends on the type of these AEs.

During induction and consolidation therapies, modifications must be done in case of non-hematologic toxicities, i.e., ADRs (pulmonary, cardiac or other non-hematologic toxicities).

During post-consolidation therapy, modifications must be done in case of hematologic and non-hematologic toxicities (pulmonary, cardiac or other non-hematologic toxicities).

If interruptions occur, missed doses of study drug will not be made up.

Study drug interruptions of greater than 28 consecutive days will require discontinuation from study treatment, unless the patient undergoes HSCT as in that case the drug interruption can be longer than 28 consecutive days (please refer to section 6.1.1 for more detailed information).

Cytarabine

Doses will be modified only during the consolidation phase with intermediate-dose cytarabine and in case of neurotoxicity, hematology and non-hematology toxicity. Please refer to [Table 6-2](#).

Idarubicin/ Daunorubicin

Doses will be modified during induction phase in case of hepatotoxicity, hematology and non-hematology toxicity. Please refer to [Table 6-2](#).

[figure not shown]
[figure not shown]
[figure not shown]

Table 6-2 Criteria for dose reduction/interruption and re-initiation of midostaurin/placebo, daunorubicin/idarubicin and cytarabine treatment for adverse drug reactions

[figure not shown]
Dose modifications for midostaurin/placebo	
Hematologic toxicities	

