10.5.3 Safety objectives

10.5.3.1 Analysis set and grouping for the analyses

For all safety analyses, the safety set will be used. All listings and tables will be presented by treatment group.

The overall observation period will be divided into three mutually exclusive segments:

1. Pre-treatment period: from day of patient's informed consent to the day before first dose of study treatment
2. On-treatment period: from day of first dose of study medication to 30 days after last dose of study medication
3. Post-treatment period: starting at day 31 after last dose of study medication.

The safety summary tables will include only assessments collected within 30 days after study treatment discontinuation and assessments prior to the data cut-off date for ongoing patients, unless otherwise specified.

All data, regardless of observation period, will be listed and assessments collected in the pretreatment and post-treatment period will be flagged in all the listings.

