8.3.9 Hematopoietic stem cell transplantation (HSCT)

Patient moving to HSCT will be reported by treatment phase. HSCT in CR or CRi with adequate blood count recovery and relapse/induction failure will be distinguished in the analysis. HSCT analyses will be based on the FAS.

9 Safety analyses

All safety analyses will be based on the safety set. Safety summaries (tables, figures) include data from the on-treatment period see ([Section 3.5.2](#)). Safety data will be presented in listing for patients who started treatment but were not randomized.

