9.2 Adverse events (AEs)

Reporting of AEs

All AEs recorded during the study will be listed and summarized. AEs will be summarized via treatment group by presenting the number and percentage of patients having at least one AE (regardless of study drug treatment in each primary system organ class) and for each preferred term using MedDRA coding (MedDRA version 22.0 or later will be used). A patient with multiple occurrences of an AE will be counted only once in the respective AE category.

AE summaries will be presented by primary system organ class, preferred term, and maximum CTC grade (CTCAE version 5.0 will be used). A patient with multiple CTC grades for an AE category will be summarized under the maximum CTC grade recorded for the event.

AE summaries will include all treatment-emergent AEs starting on or after Study Day 1 (i.e. on or after the day of the first intake of study treatment) and starting no later than 30 days after study treatment discontinuation.

AE summaries

The following incidences of AE summaries will be produced by treatment group:

- AEs regardless of study drug relationship by primary system organ class and preferred term.
- AEs regardless of study drug relationship by primary system organ class and preferred term by age (< 60 vs. => 60 years).
- AEs regardless of study drug relationship by primary system organ class, preferred term and anthracyclin.
- AEs regardless of study drug relationship by primary system organ class, preferred term, anthracyclin and age(<60 vs. >= 60 years)
- AEs with suspected relationship to study drug by primary system organ class and preferred term.
- Deaths by primary system organ class and preferred term.
- Deaths by primary system organ class and preferred term and age (<60 vs. >= 60 years)
- Deaths by primary system organ class and preferred term with Idarubicin /Daunorubicin during Induction
- Deaths by primary system organ class and preferred term and age with Idarubicin /Daunorubicin during Induction (<60 vs. >= 60 years)Deaths by primary system organ class and preferred term after Hematopoietic stem cell transplantation (HSCT)
- SAEs regardless of study drug relationship by primary system organ class and preferred term
- SAEs with suspected relationship to study drug by primary system organ class and preferred term
- Non-SAEs by primary system organ class and preferred term
- SAEs with fatal outcome by primary system organ class and preferred term

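### Adverse events starting more than 30 days into a transplant interruption enter the AE, SAE and laboratory summaries only if the patient later restarts study drug

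*SAP*

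**What the plan says.** SAP 3.6.2 defines on-treatment data by a single interval: "Date of first administration of study treatment; date of last administration of study treatment +30 days], i.e., inclusive lower and upper limit". SAP 3.6 fixes the end of that interval as "the last date when a non-zero dose of any component of study treatment was administered", so any later dose moves it forward. Protocol 10.5.3.1 divides time in the same way: "Post-treatment period: starting at day 31 after last dose of study medication".

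The opening of SAP section 9 applies the window to the safety outputs: "Safety summaries (tables, figures) include data from the on-treatment period". SAP 9.2 limits the AE summaries to events "starting no later than 30 days after study treatment discontinuation", and SAP 9.3 uses on-treatment laboratory values.

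The design builds a long drug-free gap into the course of transplanted patients. Protocol 4.2.2: "Study treatment will be interrupted at least 48 hours before the initiation of the transplant conditioning regimen". Protocol 4.2.3: "Post HSCT post-consolidation therapy will begin >30 days but not later than 100 days following HSCT". Protocol 6.3.1 ends treatment after an interruption of more than 28 days, "unless the patient undergoes HSCT as in that case the drug interruption can be longer than 28 consecutive days". None of the safety definitions makes an exception for this gap.

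**The concern.** When a patient restarts after transplant, the date of last administration moves forward and the whole drug-free gap becomes on-treatment in retrospect. When a patient does not restart, the window stays closed from 30 days after the last pre-transplant dose. Two identical events on the same day of the gap can therefore be handled differently because of something that happens afterwards.

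Restart is not a neutral marker. Under protocol 6.1.1.1 it requires blood count recovery after HSCT, and it requires that the patient is alive. An AE that starts in the late part of the gap and kills the patient before restart cannot appear in the AE, SAE or fatal-SAE summaries. A non-fatal event on the same day appears if the patient goes on to restart. The tables by arm therefore contain some transplant toxicity, selected by later outcome.

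Restart could also have depended on arm. SAP section 1 reports that investigators were unblinded after the futility stop and that some patients chose to continue. Anyone in a transplant gap at that time would have decided on restart knowing the assignment.

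**Working it through.** The plan states no figure on this point, so there is none to reproduce. The check is date arithmetic on the plan's rules.

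**Inputs**
- On-treatment tail: 30 days after the last dose, limit included (SAP 3.6.2).
- Stop before conditioning: 2 days, the minimum in protocol 4.2.2.
- Restart: day *r* after transplant, from 31 to 100 (protocol 4.2.3). Protocol 4.2.2 words the lower limit as not before 30 days, which would lower the smallest results by one day.
- Conditioning length *c*: **an assumption**. Protocol 4.2.2 leaves conditioning to local standards. I use 5, 7 and 10 days, with 0 as an extreme.

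**Formulas** (day 0 = last pre-transplant dose, T = day of transplant)
- T = 2 + c
- Drug-free days for a restarter = 2 + c + r − 1
- Last counted day for a non-restarter = day 30 = T + (28 − c)
- Affected stretch = drug-free days − 30

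| c (assumed) | Non-restarter's window closes | Gap, restart T+31 | Affected | Gap, restart T+100 | Affected |
|---|---|---|---|---|---|
| 0 | T+28 | 32 | 2 | 101 | 71 |
| 5 | T+23 | 37 | 7 | 106 | 76 |
| 7 | T+21 | 39 | 9 | 108 | 78 |
| 10 | T+18 | 42 | 12 | 111 | 81 |

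For c = 5 to 10 the affected stretch is 7 days (2 + 5 + 31 − 1 − 30) to 81 days (2 + 10 + 100 − 1 − 30). A non-restarter has 30 of those gap days counted: 30/37 = 81% at the short end and 30/111 = 27% at the long end. If dosing stops more than 48 hours before conditioning, the gap lengthens and the non-restarter's window closes earlier relative to T.

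**Worked events at c = 7 (T = day 9)**
- AE at T+10 (day 19) or T+21 (day 30): counted for both patients.
- AE at T+22 (day 31), T+45 (day 54) or T+80 (day 89): counted for a patient who restarts at T+100, not for one who never restarts.

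**Does other wording close the gap?** SAP 9.2 keys its cut-off to treatment discontinuation, which the protocol glossary defines as permanent stopping. A transplant interruption followed by restart is not a discontinuation, so 9.2 gives the same result as 3.6.2, provided a non-restarter's discontinuation date is taken as the last dose.

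**Are the events at least collected?** Not reliably for non-restarters. Protocol 8.1.1 requires AE monitoring for at least 30 days after the last dose. Protocol 8.2.2 asks for later SAEs only when a causal relation is suspected.

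**The case against.** The strongest points on the other side are these.

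- **The first 30 days off drug are covered for everyone.** A reader might infer that every AE in the transplant gap depends on restart. It does not: the 30-day tail captures conditioning and the early post-transplant days (to about T+18 to T+23 on the assumed timings), including in patients who die. This stands, and it limits the point to later events.
- **Deaths are tabulated.** A reader might infer that fatal transplant toxicity vanishes from the report. SAP 9.1 summarises all fatal cases, on-treatment and post-treatment, by arm and by system organ class and preferred term. SAP 9.2 adds deaths after HSCT, and protocol 10.5.3.2 has out-of-window AEs listed and flagged. This stands. Nor is it true that no fatal event from the late gap can be counted in the AE tables: inclusion follows the AE start date, so an event that starts in the gap, persists to restart and later proves fatal is in the window. But death tables and listings do not repair the AE, SAE or laboratory comparisons.
- **The SAP follows the protocol, and the time for redefinition was late.** The continuous window is the protocol's own, and this SAP was written after unblinding. This stands as a reason to document a change openly, not as a reason to leave the rule without comment.
- **A table of the gap would itself be incomplete,** because late AEs in non-restarters need not have been collected. This stands and must be stated with the table.

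**Conclusion.** The point holds for AEs starting more than 30 days after the last pre-transplant dose and before restart, and for laboratory values in the same stretch. Their entry into the AE, SAE and laboratory summaries depends on whether the patient later survives and restarts. The stretch is about 7 to 81 days per restarting patient, given the 48-hour minimum stop, restart at T+31 to T+100, and conditioning assumed at 5 to 10 days.

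A reader might go on to infer that the arm comparison of AEs is biased. The documents do not support that step. They give neither the number of transplanted patients nor restart rates by arm, so neither the size nor the direction of any between-arm effect can be computed. Unequal restart, whether from intolerance or from decisions made after unblinding, is possible but not shown. This is a worthwhile, inexpensive improvement to the safety definitions; it does not invalidate the safety analysis.

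**What to change.** 1. In SAP 3.6.2, for patients with HSCT, close the on-treatment window 30 days after the last pre-HSCT dose and reopen it at the first post-HSCT dose. Restarters and non-restarters are then treated alike in the main tables.
2. Show events in the interval between in a separate descriptive HSCT-period table by arm, split by restart status. Add a footnote that collection in non-restarters was limited (protocol 8.1.1 and 8.2.2), so the two groups should not be compared as if equally observed.
3. Align the cut-off in SAP 9.2 with the new wording, and correct the cross-reference at the start of SAP section 9, which points to 3.5.2 where the definition is in 3.6.2.
4. Record the change in SAP section 11, which now declares no departure from the protocol. State that it alters the definition in protocol 10.5.3.1 and was made after unblinding. The table under the present window can be kept for comparison.

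Cost: one revised definition, one extra table and fewer events in the main AE table. Dosing dates are on the exposure eCRF, and SAP 8.3.9 already reports HSCT by treatment phase, so no new data are needed. The change cannot recover late AEs that were never collected in non-restarters.
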